## **4.2 Exclusion Criteria**

**4.2.1** Any kind of malabsorption syndrome significantly affecting gastrointestinal function, including history of Crohn's disease or inflammatory bowel disease.

**4.2.2** Concurrent anti-cancer therapy (chemotherapy, radiation therapy, surgery, immunotherapy, hormonal therapy, biologic therapy) other than the ones specified in the protocol. Patients must have discontinued the above cancer therapies for 1 week prior to the first dose of study medication. Any investigational drugs should be discontinued 2 weeks prior to the first dose of study medication and radiotherapy must have been completed  $\geq 2$  weeks prior to initiation of study drug (Cycle 1, Day 1).

**4.2.3** Prior use of PI3K or Akt inhibitors in the metastatic setting for the treatment of cancer. These include, but are not limited to: taselisib, GDC-0941, GDC-0980, BEZ235, BKM120, LY294002, PIK-75, TGX-221, XL147, XL765, SF1126, PX-866, D-87503, D-106669, GSK615, CAL101. Patients who have received PI3K/Akt inhibitors previously for  $<4$  weeks will be eligible.

**4.2.4** Prior treatment with enzalutamide.

**4.2.5** Current or previously treated brain metastasis or active leptomeningeal disease; head imaging is required during screening in all patients to exclude the presence of central nervous system (CNS) metastatic disease.

**4.2.6** History of seizure or any condition that may predispose to seizure; history of loss of consciousness or transient ischemic attack within 12 months before day 1.

**4.2.7** Pregnant or lactating women.

**4.2.8** Insulin-dependent diabetes. Patients with Type II diabetes must meet the inclusion criteria outlined above.

**4.2.9** Uncontrolled intercurrent illness including, but not limited to:

- Ongoing or active infection requiring parenteral antibiotics

- Impairment of lung function (COPD > grade 2, lung conditions requiring oxygen therapy) or current dyspnea at rest
- Symptomatic congestive heart failure (class III or IV of the New York Heart Association classification for heart disease)
- Known Left Ventricular Ejection Fraction (LVEF) < 50%
- Unstable angina pectoris, angioplasty, stenting, or myocardial infarction within 6 months
- Uncontrolled hypertension (systolic blood pressure >160 mm Hg or diastolic blood pressure > 100 mm Hg, found on two consecutive measurements separated by a 1 or 2-week period despite adequate medical support)
- Clinically significant cardiac arrhythmia (multifocal premature ventricular contractions, bigeminy, trigeminy, ventricular tachycardia that is symptomatic or requires treatment [National Cancer Institute -Common Terminology Criteria for Adverse Events, Version 4.0, grade 3])
- QTcF  $\geq$  480 msec on screening EKG
- Known history of QT/QTc prolongation or Torsades de Pointes (TdP)
- ST depression or elevation of  $\geq$  1.5 mm in 2 or more leads
- Diarrhea of any cause  $\geq$  CTCAE grade 2
- Active autoimmune disease that is not controlled by nonsteroidal or steroidal (< 10 mg of prednisone per day) anti-inflammatory drugs or active inflammatory disease, including small or large intestine inflammation such as active Crohn's disease or ulcerative colitis, which requires immunosuppressive therapy
- Psychiatric illness/social situations that would compromise patient safety or limit compliance with study requirements including maintenance of a compliance/pill diary
- Known history of chronic liver disease including cirrhosis, current alcohol abuse, or infection with hepatitis B virus or hepatitis C virus (active or carrier) or renal failure
- Known history of chronic pancreatitis

- Conditions that affect lymphocyte counts, such as HIV infection or immunosuppressive therapy

#### 4.2.10 Use of prohibited drugs, as described in section 6.4.

### 4.3 Inclusion of Underrepresented Populations

Individuals of all races and ethnic groups are eligible for this trial. There is no bias towards age or race in the clinical trial outlined. This trial is open to the accrual of men and women.

## 5. REGISTRATION PROCEDURES

Patients must be AR positive to register for the study. Sections 5.1, 5.2, and 5.3 describe how AR testing can be done. Once AR positivity is confirmed, all patients MUST be registered with the Vanderbilt-Ingram Cancer Center (VICC) prior to the start of protocol treatment (see Section 5.4). Each participating site must also be registered with their own institution according to their institutional guidelines prior to start of protocol treatment.

### 5.1 Pre-Screening

Patients with TNBC may submit archival tissue to test for AR expression. A separate prescreening consent will be available to enable testing of archival tissue for AR expression before initiating other screening activities. Patients must sign the separate prescreening consent form if AR status is not already known (see section 5.2). Study site personnel must document the informed consent process for tissue analysis in the patient's clinical record.

If archival tissue is not available for AR analysis and the patient is otherwise eligible for the study and willing to go on study within 4 weeks, the patient may undergo a biopsy of metastatic site to assess AR status after signing the prescreening consent (see Section 5.3). The prescreening consent form allows extra study-related research biopsy specimens to be obtained so that the patient would not have to undergo a repeat biopsy at baseline for study purposes. Patients must be informed that analysis of tissue will not guarantee eligibility for this study, as patients found to have AR+ disease must meet all other eligibility criteria at the time of enrollment.

### 5.2 AR testing for registration

**AR testing can be performed on a prior breast cancer biopsy (primary or local recurrence), surgical specimen, or biopsy of a metastatic site.**

- For participants who are known to have androgen receptor-positive triple negative breast cancer by local testing in a CLIA certified lab on any one of the above samples (primary, local recurrence or metastasis), after discussion with the Protocol Chair, the prescreening consent does not need to be signed and he/she can sign the main consent form to proceed with eligibility screening. Patients who are found to be AR negative upon central review at Vanderbilt will be considered screen failures.

- For participants in whom androgen receptor status is not known upfront and who have archival tissue for testing: participants can sign the prescreening AR testing consent form to allow for AR testing. Please send:
  - A tissue block to the address below and indicate on the requisition that AR testing needs to be performed for registration.OR
  - If a participating institution does not allow release of formalin-fixed paraffin-embedded tissue blocks, send 3 unstained slides cut, 5  in each, on charged (plus) slides for AR testing by immunohistochemistry.
- For participants who are undergoing biopsy of a metastatic site as standard of care or specifically for AR testing: participants can sign the prescreening AR testing consent form to allow for AR testing from the biopsy, and to obtain the extra biopsies required for the study so that the participant would not have to undergo another biopsy if he/she is found to AR+ and qualifies for the study. Tissue must be sent to Vanderbilt-Ingram Cancer Center, along with the tissue block registration form for central testing of androgen receptor. See section 9 of the protocol for details on what should be obtained. Please note that a patient can only undergo a biopsy specifically for AR testing for this study if he/she otherwise meets all eligibility criteria and is able to go on study within 4 weeks of obtaining the AR results.
- The coordinating center must be notified if a sample is being sent for AR testing (see lab manual for details). Once the tissue to be tested is received at Vanderbilt, AR testing results will be provided to the ordering institution within 7-10 days. If the patient is AR+, the patient will be eligible to sign the treatment consent form and continue screening for protocol participation; the steps in section 5.4 should be followed.

Outside sites should ship specimens along with Tissue Registration Form directly to:

### 5.3 Biopsy of metastatic lesion

After signing informed consent for the research biopsy, potential participants should have 2-3 paraffin-embedded diagnostic core biopsy specimens and 2-3 core biopsy specimens suspended in RNAlater solution from a metastatic site if reasonably safe submitted prior to randomization.

Please see section 9 for further details. If AR status has already been confirmed centrally on a prior biopsy, tissue from the metastatic biopsy needs to be available, but not evaluated centrally, prior to beginning treatment on study.

Outside sites should ship specimens along with Tissue Registration Form directly to:

**For all tissue and blood/plasma:**

[REDACTED]

**5.4 Ship ALL paraffin material, RNAlater tubes or slides as detailed in the lab manual.  
\*\*Specimens should be mailed to arrive at VUMC from Monday 8AM through  
Friday 1PM\*\*Registration**

Once patients are confirmed to AR positive and if they meet all other eligibility criteria, patients will be centrally registered with the Vanderbilt-Ingram Cancer Center (VICC) at study entry by emailing the Multi-Institutional Team at [[contact]](mailto:[contact]). At the time of registration, the following documents must be emailed to the VICC CTSR office ([[contact]](mailto:[contact])):

- Copy of the patient's signed and dated Informed Consent including documentation of the consent process
- Patient Enrollment Form
- Eligibility Checklist including source documents to verify eligibility

Prior to registration a copy of IRB approval at the respective sites will be requested and on file at VICC.

CTSR requests 24-48 hours to review all documents and confirm eligibility. [REDACTED]

In the phase II portion, the VICC Coordinating Center will assign sequence numbers to all patients in screening. Only patients deemed eligible will be randomized to a treatment arm. Sequence numbers will not be re-used if a patient screen fails. The Center will randomize eligible patients to enzalutamide + tasisib or enzalutamide alone. Following registration and randomization (after AR results are released to the treating institution, see below), eligible participants should begin protocol treatment within 2 weeks. Issues that would cause treatment delays should be discussed with the Protocol Chair. If a participant does not receive protocol therapy following randomization within allowed time period, the participant will become ineligible and will be cancelled from the study. Such patients will have to undergo screening

again to participate in the study in the future. Any requests for eligibility exceptions and/or deviations must be approved in writing by the Protocol Chair and the local IRB prior to execution. As is generally accepted, standard of care procedures performed prior to consent, but within the protocol defined screening window for each assessment can be used for study purposes. All research only procedures must be performed after the consent date.

## 6. TREATMENT PLAN

### 6.1 Overview

This is an open-label phase Ib/II multi-institution trial that evaluates the safety profile and anti-tumor activity of enzalutamide +/- taselisib in patients with androgen receptor positive metastatic triple negative (ER negative, PR negative, HER2Neu negative by IHC or FISH) breast cancer (AR+ TN MBC).

As taselisib has not been evaluated with enzalutamide, we will proceed with a phase Ib portion to ensure safety of the combination prior to open enrollment on the study.

### 6.2 Phase Ib component of the trial

The phase Ib component is complete. The primary objective of this portion of the trial was to determine the safety profile [dose-limiting toxicities (DLTs) during the first cycle of treatment, and maximum tolerated dose (MTD)] of the combination of taselisib and enzalutamide. The phase Ib portion allowed patients who are estrogen and/or progesterone receptor positive or negative, provided they are HER2 negative (see eligibility criterion 4.1.5).

- Enzalutamide + taselisib: the taselisib dose will start at 2 mg (dose level 1). Dose escalation proceeded among cohorts of 3 patients according to a standard 3+3 algorithm beginning at the lowest dose level.

In addition, pharmacokinetic (PK) sampling was collected from patients enrolled into the Phase Ib part of the study to allow for comparison within the study and to previous observations when taselisib was administered as a single agent in the Phase Ia trials. All open sites were able to participate in the phase Ib component.

#### 6.2.1 Phase I Agent Dose Escalation

Dose level	Enzalutamide	Taselisib
1	160 mg PO daily	2 mg PO daily

2	160 mg PO daily	4 mg PO daily
3	160 mg PO daily	6 mg PO daily
4	160 mg PO daily	8 mg PO daily

**1 cycle = 28 days**

All pills were self-administered (by the patients themselves). A pill diary was given to all patients enrolled in the study. The investigator will instruct the patient to take the study drugs exactly as specified in the protocol. Taselisib and enzalutamide were administered on a continuous once daily dosing schedule. To assist in PK assessment, for patients enrolled in the combination arm (phase Ib or II) at Vanderbilt only, taselisib was started on day 1, and enzalutamide was added on day 9.

### 6.2.2 Definition of Dose-Limiting Toxicity (DLT)

Any of the following events that occur during Cycle 1 (first 4 weeks) was considered a DLT when possibly, probably or definitively classified as drug-related (according to NCI CTCAE v 4.0 Requirements). Whenever a patient experienced toxicity that fulfilled the criteria for a DLT, treatment with taselisib was held and the toxicity was followed up, Dose reductions as listed in Section 7.1 were followed. No DLTs were noted in the phase Ib.

Toxicity	DLT criteria	Follow-Up Evaluation
Hematologic	
 
Anemia CTCAE Grade <math>\geq 3</math> will not be considered a DLT unless judged to be a hemolytic process secondary to study drug.
 
Febrile neutropenia CTCAE Grade <math>\geq 3</math>
 
ANC CTCAE Grade 3 for <math>> 7</math> consecutive days. G-CSF use is permitted during the DLT window.
 
ANC CTCAE Grade 4
 
Platelet count CTCAE Grade 3 for <math>> 7</math> consecutive days and/or with signs of excessive bleeding
 
Platelet count CTCAE Grade 4
 
	
If <math>\geq</math> CTCAE grade 3 neutropenia or <math>\geq</math> CTCAE grade 3 thrombocytopenia have been demonstrated, these parameters must be repeated at least once a week until resolution to <math>\leq</math> CTCAE grade 1 neutropenia or <math>\leq</math> CTCAE grade 1 thrombocytopenia to allow for initiation of re-treatment, and then at least weekly until either resolution or until stabilization.

Table 1: DLT criteria and Follow-up Evaluation (CTCAE v 4.0)		
Toxicity	DLT criteria	Follow-Up Evaluation
Cardiac disorders	
 
• Cardiac toxicity CTCAE Grade <math>\geq 3</math> or cardiac event that is symptomatic or requires medical intervention
 
• Clinical signs of cardiac disease, such as unstable angina or myocardial infarction, or Troponin CTCAE Grade 3 (confirmed with a repeat Troponin within 24 hrs)
 
• ECG QTc interval prolonged CTCAE Grade <math>\geq 3</math> (after repeat confirmation on at least 2 more ECGs at the same time point)
 
	
Patients who experience ECG abnormalities indicative of an ischemic cardiac event should be evaluated by cardiology and have ECGs repeated at least once a week until normalization or stabilization of ECG findings.
 
If troponin <math>\geq</math> CTCAE grade 3 has been demonstrated, the patient should be evaluated by cardiology and this parameter must be repeated once a week or as clinically indicated until resolution to <math>\leq</math> CTCAE grade 1, and then at least weekly until either resolution or until stabilization.
 
Patients who experience QTc prolongation should be followed as per Dose Modification section guidelines and should be evaluated by cardiology.

Vascular disorders/ Hypertension	Persistent hypertension CTCAE Grade $\geq 3$ requiring more than one drug or more intensive therapy than previously	
Fatigue	Fatigue CTCAE Grade 3 for $> 7$ consecutive days	
Rash and/or photosensitivity	Rash or photosensitivity CTCAE Grade 3 for $> 7$ consecutive days despite skin toxicity treatment, including oral steroid and antihistamines Photosensitivity CTCAE Grade $\geq 4$	Rash should be evaluated weekly until resolution.

Table 1: DLT criteria and Follow-up Evaluation (CTCAE v 4.0)		
Toxicity	DLT criteria	Follow-Up Evaluation
Endocrine: Hyperglycemia	
 
• Hyperglycemia Grade 3 (FPG 250 – 399 mg/dL; 13.9 - 22.2 mmol/L) (confirmed with a repeat FPG within 24 hrs) for > 7 consecutive days despite oral anti-diabetic treatment
 
• Hyperglycemia Grade 4 (FPG ≥ 400 mg/dL; ≥ 22.3 mmol/L)
 
• Hyperglycemia leading to diabetic keto-acidosis, hospitalization for IV insulin infusion, or non-ketotic coma
 
• Hyperglycemia occurring during corticosteroid administration will be only considered DLT if not resolved within 2 days after the end of corticosteroid treatment.
 
	
For details of the follow-up and treatment of ≥ grade 3 hyperglycemia refer to the Guidelines for the treatment of study drug-induced hyperglycemia provided in the Dose Modification Section

GI disorders	
 
• Diarrhea CTCAE Grade ≥ 3 for ≥ 48 hrs, despite the use of optimal anti-diarrhea therapy
 
• Nausea/vomiting CTCAE Grade ≥ 3 for ≥ 48 hrs, despite the use of optimal anti-emetic therapy
 
• Pancreatitis CTCAE Grade ≥ 3
 
	
If amylase and/or lipase ≥ CTCAE grade 3 (> 2 x ULN) has been demonstrated, these parameters must be assessed once at 2 to 4 days and once again at 7 days (± 1 day) and be repeated twice a week until resolution to ≤ CTCAE grade 2 to allow for initiation of re-treatment, and then at least weekly until either resolution to ≤ CTCAE grade 1 or until stabilization.
 
A CT scan or other imaging study to assess the pancreas, liver, and gallbladder must be performed within 1 week of the first occurrence of any ≥ CTCAE grade 3 of amylase or lipase. Amylase and lipase should be followed weekly until resolution to ≤ CTCAE grade 1.

Table 1: DLT criteria and Follow-up Evaluation (CTCAE v 4.0)		
Toxicity	DLT criteria	Follow-Up Evaluation
Hepatic	
 
Total bilirubin CTCAE Grade 2 for > 7 consecutive days, if less normal-grade 1 at baseline
 
Total bilirubin CTCAE Grade <math>\geq</math> 3, if grade 2 at baseline
 
AST or ALT CTCAE Grade <math>\geq</math> 2 in conjunction with blood bilirubin d CTCAE Grade <math>\geq</math> 2 of any duration
 
AST or ALT CTCAE Grade 3 for > 7 consecutive days
 
AST or ALT CTCAE Grade 4
 
Serum alkaline phosphatase CTCAE Grade 4
 
Serum lipase and/or serum amylase (asymptomatic) CTCAE Grade 3 for > 7 consecutive days
 
Serum lipase and/or serum amylase (asymptomatic) CTCAE Grade 4
 
ALT or AST of 3X ULN and concomitant bilirubin of >2 X ULN (Hy's Law) with no other explanation other than study drug should be permanently discontinued from treatment with study drug.
 
	
Both taselisib and enzalutamide should be held.
 
If total bilirubin <math>\geq</math> 2 x ULN or <math>\geq</math> CTCAE grade 3 AST/ALT has been demonstrated, these parameters must be repeated at least twice a week until resolution to <math>\leq</math> CTCAE grade 1 (or <math>\leq</math> grade 2 for AST or ALT, if liver metastasis are present) to allow for initiation of re-treatment, and then at least weekly until either resolution or until stabilization.
 
Patients with total bilirubin > ULN (any duration) should have fractionation of bilirubin into total/direct or indirect/direct components and any additional work-up as clinically indicated by these results. Follow-up of hyperbilirubinemia should proceed as per the guidelines above, irrespective of the results of fractionation.
 
For any hepatic toxicity CTCAE Grade 4, or CTCAE Grade 3 that does not resolve within 7 days to CTCAE Grade <math>\leq</math> 1 (or CTCAE Grade <math>\leq</math> 2 if liver infiltration with tumor present), an abdominal CT scan should be performed to assess if it is related to disease progression.

Renal	Serum creatinine CTCAE Grade $\geq$ 3	
If serum creatinine <math>\geq</math> 3 x ULN has been demonstrated, this parameter must be repeated at least twice a week until resolution to <math>\leq</math> CTCAE grade 1 to allow for initiation of re-treatment, and then at least weekly until either resolution or until stabilization.
 
Serum creatinine <math>\geq</math> 2.0 x ULN and [+3] proteinuria or hematuria <math>\geq</math> CTCAE grade 2 has been demonstrated, a 24-hour urine collection for total protein and total creatinine must be done at least weekly until either resolution to baseline value or until stabilization. Whenever a measured CrCl is obtained, a serum creatinine should

Table 1: DLT criteria and Follow-up Evaluation (CTCAE v 4.0)		
Toxicity	DLT criteria	Follow-Up Evaluation
		be obtained within $\leq 72$ hours of the urine collection.
Other hematologic and non-hematologic toxicities	Any other CTCAE $\geq$ Grade 3 toxicity except: 
 
• Lymphocyte count decreased (lymphopenia) CTCAE grade <math>\geq 3</math> unless clinical significance
 
• Alopecia of any grade
 
	Patients who experience neurotoxicity should be followed as per Dose Modification Section  Patients who experience non-laboratory DLTs must be evaluated at least once a week following demonstration of the toxicity until resolution of the toxicity to allow for re-treatment, stabilization of the toxicity, or study treatment completion.
Apart from the criteria listed above, if a lower grade AE leads to a dose interruption of taselisib of more than 7 consecutive days, this AE may be considered as a DLT. Such cases will be considered individually. Patients who withdraw or are withdrawn from the study prior to completing the DLT assessment window for any reason other than a DLT or miss $> 7$ days for non-drug related AEs will be replaced.		

The following were instructions for DLTs in the phase Ib. Patients who meet DLT criteria must stop taselisib. Patients who meet DLT criteria for hepatotoxicity should hold both taselisib and enzalutamide. Patients whose treatment is interrupted or permanently discontinued due to an adverse event or clinically significant laboratory value must be followed as outlined in the table above, at least once a week for 4 weeks, and subsequently at 4-week intervals, until resolution or stabilization of the event, whichever comes first. Patients that require a dose delay of  $> 28$  days due to a cause unrelated to study participation will have the opportunity to continue study if deemed appropriate to do so by the Protocol Chair of the study. If patients experience a DLT considered related to taselisib, the patient may remain on enzalutamide on-study after resolution of the DLT at the discretion of the treating physician after receiving counseling about alternate treatment options. If patients experience a DLT considered related to enzalutamide, they have the option of remaining on single agent GDC0032 on-study at the discretion of the treating physician after receiving counseling about alternative treatment options. After resolution of the DLT, patients may be able to restart taselisib or enzalutamide at a lower dose at the discretion of the treating physician. However, such cases will be considered a DLT for the purposes of defining the MTD. All patients who continue taking taselisib and/or enzalutamide as a single agent will not be evaluable.

Patients who withdraw or are withdrawn from the study prior to completing the DLT assessment window for any reason other than a DLT or miss  $\geq 7$  days for non-drug related AEs will be replaced. This includes patients whose disease progresses within 30 days of starting the study. Patients requiring dose reduction of enzalutamide or taselisib for reasons other than a DLT in cycle 1 of the phase Ib portion will not be included in the DLT evaluation. After the MTD is reached,

patients in the phase Ib on lower dose levels can dose escalate to the MTD at the discretion of the treating physician and after discussion with the Protocol Chair.

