### 6.2.3 Definition of Maximum Tolerated Dose (MTD)

The MTD was defined as the highest dose of taselisib tested in which a DLT is experienced by 0-1 out of 6 patients among the dose levels. The dose of enzalutamide remained constant. The first cohort of patients (3 patients) in each arm started at dose level 1, and each patient was observed for 4 weeks on the specified dose and instructions were followed as below:

- If no patient in the first cohort of 3 experiences a DLT, dose escalation will proceed and patients will be accrued at the next dose level. If 1 of these patients experiences a DLT, the cohort will be expanded to 6 patients. If <33% of these patients experiences a DLT (e.g., 1 of 6 patients), dose escalation may proceed.
- If a DLT is observed in  $\geq 33\%$  of the patients in a given cohort (e.g.  $\geq 2$  of 6 patients), the MTD will have been exceeded and the lower dose level will be evaluated.

An exception to the above rule would be in the case in which the two DLTs observed out of 6 patients are both hematologic in nature and potentially reflect poor bone marrow reserve in this heterogeneous patient population and not the true MTD for the combination. In this instance, up to 3 additional patients may be enrolled to expand the total cohort size to 9 patients to assess for further DLT. In this situation, if a third DLT is observed, the MTD will have been exceeded and the lower dose level will be evaluated.

- If the 2 mg dose does not exceed the MTD, then dose escalation will proceed to the 4 mg dose. If the 4 mg dose does not exceed the MTD, then dose escalation will proceed to the 6 mg dose, and if the 6 mg dose does not exceed the MTD, then dose escalation will proceed to the 8 mg dose. If <33% of patients experience a DLT in the 8 mg cohort, then this dose level will be the maximum administered dose (MAD).

No new cohort of patients will be treated until the previous cohort has been fully evaluated for toxicity. Patients requiring dose reduction for reasons other than a DLT in cycle 1 of the phase Ib portion will not be included in the DLT evaluation. If the frequency of Grade 3 or 4 toxicities or other unacceptable lower grade chronic toxicities in the phase 1b portion suggests that the MTD has been exceeded at that dose level, any remaining accrual at that dose level will be halted and a lower dose of taselisib may be examined.

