Grade 3: first event	
 
Hold dose and monitor closely for changes in severity and for hypersensitivity-related systemic symptoms
 
Recommend topical steroidsc
 
Recommend initiating oral steroids unless contraindicatedd
 
Upon resolution to <math>\leq</math> Grade 1, reduce to next lower dose level
 
Consider dermatological consultation
 
Consider obtaining photographs of rash if permitted by local regulations
 

Grade 3: first recurrence after dose reduction	
 
Hold dose and monitor closely for changes in severity and for hypersensitivity-related systemic symptoms
 
Recommend initiating oral steroids unless contraindicatedd
 
Discuss with Protocol Chair if would like to consider restarting at next lower level upon resolution to <math>\leq</math> Grade 1, or permanently discontinue
 
Recommend dermatological consultation, if not already performed
 
Consider obtaining photographs of rash if permitted by local regulations
 

Recurrent Grade 3 or Grade 4	
 
Manage as described above.
 
Discontinue taselisib permanently.
 

Hyperglycemia	
For all grades	
 
Instruct patient to follow dietary guidelines provided by the American Diabetes Association
 
For <math>\geq</math> grade 2, initiate, continue or intensify medication with appropriate anti-diabetic treatment (Note: some oral anti-diabetic drugs are CYP3A inducers or inhibitors and should be used with caution)
 
Metformin is the first antihyperglycemic medication of choice because of the lower risk of hypoglycemia with this agent. Because metformin in some patients may also cause diarrhea and not be well tolerated, other antihyperglycemic medications such as sulfonylureas (e.g., glimepiride, glipizide) can be used. Extra caution should be used with other drugs such as sulfonylureas because of the increased risk for hypoglycemia with these agents. Consultation with an endocrinologist can be helpful in managing hyperglycemia.
 
If Grade worsens start following recommendations for the worsened grade
 

Grade 1	
 
Maintain dose level, check FPG every week for 2 weeks, then continue checking every 2 weeks until resolved
 

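### Phase Ib patients whose dose is cut in cycle 1 for drug-related toxicity short of a DLT are dropped from the DLT evaluation, so the tally excludes patients because of the tolerability it is meant to measure

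*Combined protocol and SAP*

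**What the plan says.** The exclusion appears twice. On the DLT evaluation, Section 6.2.2 says that patients who need "dose reduction of enzalutamide or taselisib for reasons other than a DLT in cycle 1 of the phase Ib portion will not be included". Section 6.2.3 says: "Patients requiring dose reduction for reasons other than a DLT in cycle 1 of the phase Ib portion will not be included". Neither sentence separates drug-related from unrelated reductions.

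Several DLT lines in Table 1 require a minimum duration. Grade 3 rash must last more than 7 "consecutive days despite skin toxicity treatment, including oral steroid and antihistamines". Grade 3 fatigue and grade 3 AST or ALT also need more than 7 consecutive days. Diarrhea of grade 3 or higher needs at least 48 hours despite optimal therapy.

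The dose rules in Section 7 do not carry those durations. For a first grade 3 rash, Table 3 holds taselisib and, on resolution to at most "Grade 1, reduce to next lower dose level".

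The closing row of Table 1 adds that when any "lower grade AE leads to a dose interruption of taselisib of more than 7 consecutive days, this AE may be considered as a DLT". Section 6.2.3 defines the MTD as the highest dose at which "a DLT is experienced by 0-1 out of 6 patients among the dose levels"; Section 15.2 words it as 0 of 3 or 1 of 6. The reported result is "No DLTs were noted in the phase Ib".

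**The concern.** Safety and tolerability of the combination is the phase Ib primary objective (Section 2.1). A patient whose dose was cut in cycle 1 because of drug toxicity gives direct evidence on that objective and is among those most likely to have met a DLT line had full dosing continued. Removing that patient makes membership of the evaluable set depend on the outcome being assessed.

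The text is also asymmetric. For missed days, Section 6.2.2 limits replacement to adverse events that are not drug-related, but it draws no such line for reductions. A lower-grade event managed by a taselisib interruption of more than 7 days may be called a DLT; managed by a dose reduction, it takes the patient out of the evaluation.

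At stake are the count that governs escalation and the meaning of the zero-DLT summary, which is part of the basis for the phase II dose in Section 6.3.

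**Working it through.** **1. The plan's own size.** Section 15.4 expects 15 phase Ib patients and at most 24. Four levels of 6 give 4 × 6 = 24. Four levels of 3 plus one expansion of 3 give 4 × 3 + 3 = 15. Both reproduce under a standard 3+3. No stated figure is disputed.

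**2. Can a toxic reduction miss the DLT line?** Set side by side:

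| Toxicity | DLT only if (Table 1) | Dose rule (Section 7) |
|---|---|---|
| Rash, grade 3 | more than 7 days despite treatment | Table 3, first event: hold, then one level lower |
| Fatigue, grade 3 | more than 7 days | Table 3, other toxicities: hold, then one level lower |
| Diarrhea, grade 3 | at least 48 hours despite optimal therapy | Table 3, first occurrence: hold, then one level lower |
| AST/ALT, grade 3 | more than 7 days (any grade 2 or higher counts if bilirubin is also grade 2 or higher) | 7.2.1.5: above 3 × ULN, hold, then reduce |

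Section 7.4 also lets the investigator reduce for toxicity of any grade or duration. So the case is reachable.

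It does not extend to every Table 1 line. Grade 3 hematologic toxicity that resolves within 7 days resumes at the current dose, and a first asymptomatic grade 3 hyperglycemia may restart at the same dose (Table 3). Table 1's final row makes most other grade 3 or higher toxicities DLTs outright.

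**3. Effect on escalation.** Let d be the per-patient DLT rate and r the rate of drug-related, non-DLT cycle 1 reductions. The documents give neither; both are assumptions. If the event rate seen by the algorithm is q, a level passes with 0 of 3, or with 1 of 3 followed by 0 of the next 3:

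P(pass) = (1 − q)³ + 3q(1 − q)⁵

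- As written, with excluded patients replaced: q = d/(1 − r). Replacement is an assumption, because 6.2.2 names as replaced those who leave early or miss days, not those whose dose is reduced.
- Reductions counted as events: q = d + r.
- Kept in the denominator as non-events: q = d.

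For d = 5% and r = 30%, as written q = 0.05/0.70 = 0.0714 and P = 0.801 + 0.148 = 0.949. Counted as events, q = 0.35 and P = 0.275 + 0.122 = 0.396.

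| d | r | As written | Counted as events | Kept as non-events |
|---|---|---|---|---|
| 5% | 10% | 0.968 | 0.814 | 0.973 |
| 5% | 20% | 0.960 | 0.600 | 0.973 |
| 5% | 30% | 0.949 | 0.396 | 0.973 |
| 10% | 10% | 0.887 | 0.709 | 0.906 |
| 10% | 20% | 0.862 | 0.494 | 0.906 |
| 10% | 30% | 0.828 | 0.309 | 0.906 |

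The last column matters. Exclusion with replacement is slightly stricter than keeping these patients as non-events, so restoring them to the denominator does not correct the tally. The distortion exists relative to counting them as events.

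In a single cohort, three DLT-free evaluable patients plus one excluded toxic reduction become 1 of 4 (25%) when it is counted. With two excluded, the count is 2 of 5 (40%), above the 33% limit in 6.2.3.

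**4. Neighbouring limits.** Table 1's closing row replaces patients who miss more than 7 days for non-drug-related events; the text after the table says 7 or more. A patient who misses exactly 7 days is treated differently by the two. The early-leaver rule then adds: "This includes patients whose disease progresses within 30 days of starting the study". The DLT window is cycle 1, which is 28 days, so a patient who progresses on day 29 or 30 has already completed it.

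**The case against.** The sponsor could answer as follows.

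- **Other clauses already protect patients.** Section 6.2.3 halts accrual at a level if grade 3 or 4 toxicity, or unacceptable lower-grade chronic toxicity, suggests the MTD is exceeded, and Table 1 lets long interruptions count. These clauses stand as safeguards, so such patients can influence the dose informally. But the halt has no numeric threshold and the Table 1 clause concerns interruptions. Neither returns a reduced patient to the tally. The provision in 6.2.2 that a restart at a lower dose still counts covers only patients who had already met a DLT line.
- **The zero-DLT statement is true.** It is. The excluded patients had no DLT by definition, so a reader who infers that the statement is false goes too far. What is missing is its denominator and the number of toxic reductions beside it.
- **There is no sign that it happened.** This also stands. The documents do not show that any patient was excluded under this rule. Section 7.2.1.3 reports no grade 3 or 4 rash in phase Ib, with escalation to 8 mg, so the rash row shows the mechanism, not an event. The 6.2.2 remark that Section 7.1 reductions were followed concerns patients who met DLT criteria, and Table 2 lists only the 4 mg starting dose. The phase Ib reduction steps are therefore not fully visible.
- **The dose did not rest on this count alone.** Correct: Section 6.3 sets 4 mg from phase Ib and from other taselisib studies. A reader might link the phase II rash cluster (7 of 8 combination patients) or the choice of 4 mg to this rule. The documents support neither inference.
- **The patients are not lost to safety reporting.** Section 15.5 keeps everyone who received study drug in the toxicity evaluation. That preserves the adverse event tables but leaves the DLT tally unchanged.

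**Conclusion.** The concern holds as a flaw in how the DLT-evaluable set is defined: the exclusion depends on the outcome and is stated twice without an exception for drug-related toxicity. Its possible size is large. At an assumed 5% DLT rate and 10% to 30% toxic non-DLT reductions, the pass probability is 0.97 to 0.95 as written, against 0.81 to 0.40 with those reductions as events. These figures rest on assumed rates, on replacement of excluded patients, and on a plain 3+3 without the hematologic expansion to 9 patients in 6.2.3.

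Its actual size in this trial is unknown and may be zero. The point should be acted on because the phase Ib tolerability result cannot be interpreted without the missing counts. It is not evidence that the phase Ib conclusion or the phase II dose is wrong. The missed-days and 30-day mismatches are real but minor, and they do not bear on toxic reductions.

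**What to change.** 1. In 6.2.2 and 6.2.3, limit the exclusion to cycle 1 reductions unrelated to study drug, and say whether excluded patients are replaced. The DLT definitions in Table 1 need not change.
2. As phase Ib is complete, report for each dose level the patients treated, excluded or replaced (with reason) and evaluable.
3. Add a sensitivity tally per dose level that counts drug-related cycle 1 reductions of either drug as events. This is the essential step, since restoring these patients as non-events would not correct the tally.
4. Keep the zero-DLT statement, but give it with the evaluable denominator and the number of patients with drug-related cycle 1 reductions.
5. Reconcile the two missed-days limits within 6.2.2, and reconcile the 30-day progression clause (also in 15.3) with the 28-day DLT window.

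The cost is wording in two sections and a recount of existing records. With no DLTs through four levels, that is about 4 × 3 = 12 evaluable patients, or 15 if one level was expanded by three, plus any who were excluded. No new data are needed. The phase Ib safety result may look somewhat less favourable if drug-related reductions turn up.
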